Aim 1: Feasibility will be assessed through examination of participant recruitment, retention and engagement. Specifically, we will look at the number of participants who refuse to participate in the pilot at the time of recruitment and the reason they declined participation. Secondary impacts of interest include: medication adherence as measured by the four-item MA Questionnaire (MAQ) and change in systolic and diastolic blood pressure at 3 months.

Aim 2: To test the acceptability of a 3-month SMS-based intervention in adults with uncontrolled hypertension. One cohort of 24 participants will be recruited for the SMS intervention. Acceptability will be assessed using the systems usability scale (a validated questionnaire that measures usability reliably in small samples)¹⁸ and eliciting free comments after the survey.

At the end of this pilot project, we will have preliminary data essential for a future formal efficacy trial, to be proposed in a subsequent application to the AHRQ.

Our **first hypothesis** is that over 50% of contacted patients will respond to SMS messages and over 50% will check HBPM. This estimate is based on previous study by Bobrow and

colleagues in a similar patient population.³ Our **second hypothesis** will be that > 75% will be satisfied with the service (OK or above on the usability survey).⁹

Methods and Measures

Design

A randomized control trial of 24 non-adherent participants will be monitored and followed for 3 months; An ambulatory BP arm device will be provided to all participants with printed instructions in English or Spanish (from the American Heart Association) on how to measure BP at home (HBPM). Patients will be instructed on checking their BP at least twice a week.^{14,19} Text messages will be generated by Twilio platform, keeping a record of participants contacted, sent and received texts. Participants in the control arm will receive standard of care education for controlling high blood pressure in clinic by their healthcare providers. They will be followed to monitor any changes in their BP throughout the duration of the study.

Study team members will identify patients with uncontrolled hypertension during clinic visits. Study team members will approach patients 18 years or older who have uncontrolled HTN (SBP>130 or DBP >80) and have 2 or more BP medication(s) on their medication list.

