recommendations by HTN guidelines, which designate a hypertensive urgency to be 180/110 mm Hg or higher and hypotension 90/60 or lower.²

Patients who no show to the follow up visits will be telephoned to assess adherence barriers. The study team member will create a telephone encounter in the electronic health record to document their discussion and route it to the patient's PCP. Patients who refuse participation in the study will be asked for the reason and their responses will be recorded to determine any barriers to participation. Study team members will attempt to contact patients who miss follow up visits every week up to 3 times, if after the 3rd time the patient is still not able to be reached, the patient will be lost to follow up.

Setting

The study team will recruit patients who fall within the eligibility criteria from Wake Forest Baptist Medical Center.

Subjects selection criteria

Eligibility and recruitment

Inclusion criteria

Patients 18 years and older who have SBP>130 or DBP >80 during an office visit encounter in the past 6 months and have BP medication(s) on their medication list.

- Own a phone with SMS capability
- Non-adherent-MAQ score of 1 to 4
- Vulnerable population (Black, Hispanic or education level < or equal high school (as an indicator of low SES)

Exclusion Criteria

- End-stage renal disease (on hemodialysis or peritoneal dialysis)
- Kidney transplant recipients
- Unable to afford BP medications or lack transportation to clinic visits
- Hospice or nursing home care
- Dementia or cognitive impairment on the problem list

Sample Size

24 patients –We will randomize 12 patients into 2 groups

Interventions and Interactions

Pilot randomized controlled study.

Participants in the SMS intervention arm will receive usual care and SMS texting and phone calls. Study team members will send secure SMS messages to participants weekly for four weeks and then every other week until their next appointment.

The secure messaging system will be as follows

Introductory message:

Welcome to managing your blood pressure with the Nephrology/ Internal medicine clinics at Wake Forest. Try to take your BP meds at the same time every day to keep your BP under control! Make it part of your daily routine:

First week

Adherence checkpoint:

1. *Good morning! Did you take your blood pressure medications today?*

“No” Response:

1. *Let's try to stay on top of taking them daily! You can do this!*

Additional prompts:

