Results will be analyzed initially using descriptive statistics. Comparison between groups will be done using chi square tests for proportions, and t-tests for continuous variables. Regression analysis will be performed to identify independent outcome predictors. RedCap will be utilized to collect all patient data. Participant's demographics (including education level), co-morbidities, number of medications, number of blood pressure medications and BP numbers will be extracted from Wake One when available. Level of education will be confirmed verbally with each participant during consent process. Only one participant identifier will appear in the data collection forms.

The full analysis set will include participants who have responded to at least one SMS message post-randomization. Descriptive statistics will be computed for each treatment group; medians and percentiles will be reported for skewed continuous variables. For primary and secondary outcomes, descriptive statistics and 95% confidence intervals will be used to summarize the differences between groups. The secondary outcome of BP and other continuous variables will be assessed with a repeated-measures analysis using a mixed linear model approach. The Wilcoxon rank sum test will be used to compare MA between groups. Hypothesis tests will be 2-sided using the 0.05 significance level. Bonferroni-type adjustments for multiple testing will be implemented to control type I errors. Statistical analysis will be performed using SAS software (SAS Institute, Cary, NC).

Treatment assignment will be determined using blocked randomization

The primary analysis will consist of all subjects who responded with at least one BP measurement

Human Subjects Protection

Subject Recruitment Methods

Subjects will be identified when they come to an office visit and their blood pressure is not well controlled. The PI clinician (internal medicine preceptors or residents) will verbally alert the study coordinator on site of possible participants based on BP >140/90. The study team member will meet the patient in a private room in 7th Janeway, determine eligibility, and signed informed consent will be obtained from each subject. Once enrolled, the subjects will be contacted by phone via SMS and phone call. To ensure equal access to participation among women and minorities we will translate all materials and questions to Spanish. The privacy of

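### With 24 participants, and at most 12 for SMS-only outcomes, the planned regression cannot reliably identify independent outcome predictors

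*Combined protocol and SAP*

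**What the plan says.** The Analytical Plan commits to the analysis in one sentence: "Regression analysis will be performed to identify independent outcome predictors". No other section narrows it. The same paragraph then lists what will be taken from the medical record: "demographics (including education level), co-morbidities, number of medications, number of blood pressure medications and BP numbers". That is a data-collection list, not a model specification.

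The Design section describes "A randomized control trial of 24 non-adherent participants will be monitored and followed for 3 months". The Sample Size section says only "24 patients –We will randomize 12 patients into 2 groups", read here as 12 per arm, and gives no power or precision basis.

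On error control, the Analytical Plan says "Hypothesis tests will be 2-sided using the 0.05 significance level" and "Bonferroni-type adjustments for multiple testing will be implemented to control type I errors". It does not say which tests form the family or whether the regression is among them.

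**The concern.** Calling a factor an independent predictor means that its association survives adjustment for the other candidates. That needs enough information to estimate several coefficients together. Here there are 24 people for outcomes measured in both arms. For engagement, defined through replies to SMS, there are at most 12.

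Two things can go wrong. Chance associations may be reported as findings, or real ones missed because the tests have little power. For binary outcomes, the model may also have no finite estimates.

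The Specific Aims present the pilot as a source of preliminary data for a later efficacy trial. A factor reported as an independent predictor, with no exploratory label, could be given more weight there than it deserves.

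**Working it through.** **Inputs from the documents.** N=24, 12 per arm; two-sided 0.05; clinic no-show rate 30%; engagement cut-off 44%. There is no derivation of the sample size to reproduce; only 2 × 12 = 24 can be checked.

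**Assumptions.** The number of predictors k is not stated. The record list names five groups, two of which (demographics and co-morbidities) can each supply several variables, so k=6–7 is plausible but assumed. Results are shown from k=2 upward. Predictors are taken as mutually independent and unrelated to the outcome. A moderate predictor is taken as f²=0.15, a partial correlation of √(0.15/1.15) = 0.36.

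**False predictors and apparent fit.** The table gives null simulations for the linear model at n=24. Expected R-squared from noise is k/(n−1) = k/23. The last column is complete separation at n=12 for event rates of 30–50%.

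| k | Any p<0.05, unadjusted, n=24 | R-squared from noise, n=24 | Complete separation, binary outcome, n=12 |
|---|---|---|---|
| 2 | about 9% | 0.09 | about 2–8% |
| 4 | about 17% | 0.17 | about 23–41% |
| 6–7 | about 24% | 0.26–0.30 | about 68–92% |

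The first column can be compared with 1 − 0.95^k for fully independent tests: 10%, 19% and 26–30%. Repeat simulations moved the k=6–7 entries by about two points. Backward elimination on pure noise at n=24 kept at least one variable in about 27% of runs at k=6 and 37% at k=8.

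**With Bonferroni.** Testing each coefficient of the full model at 0.05/k holds the chance of any false predictor to about 5% or less. Power for one moderate predictor at k=6 comes from the noncentral F distribution with noncentrality f²·n and n−k−1 residual degrees of freedom:

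- n=24, 17 residual df: 43% at 0.05; 18% at 0.05/6 = 0.0083.
- n=12, 5 residual df: 20% at 0.05; 5% at 0.0083.

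The smallest partial correlation detectable with 80% power at n=24, k=6 is 0.52 unadjusted and 0.62 with Bonferroni.

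**Binary outcomes.** No-show at 30% gives 0.30 × 24 = 7.2 events, or 7.2/6 = 1.2 to 7.2/7 = 1.0 per predictor. Engagement at 44% gives 0.44 × 12 = 5.3 events, or 5.3/6 = 0.9 per predictor. Under complete separation, ordinary logistic regression has no finite maximum-likelihood estimate. At n=24 with 30% events, separation is much rarer: about 6–16% at k=6–7. Counting quasi-complete separation as well raises the n=12 figures; at 44% events it gives 15% at k=2, 40% at k=4 and 81% at k=6.

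**Analysis sets.** The plan limits its full analysis set to those who answered an SMS, and its primary analysis to those who returned a BP reading. If the second set governed the regression and 44–50% of the 12 SMS participants qualified, it would hold 5.3 to 6 people. A model with six predictors and an intercept has seven parameters.

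**The case against.** The case on the other side has real force on certainty and size.

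- A reader might infer that the regression would yield false predictors or models that cannot be fitted. The figures do not support that. Even unadjusted at k=6–7, about three null analyses in four give no false predictor. A one-covariate linear model on 24 people can be fitted, and so can most logistic models on 24. Failure is the likely result only when a binary outcome, about 12 people and six or more predictors occur together.
- The plan promises a Bonferroni-type adjustment. If it covers the regression, the unadjusted rates do not apply. This stands, and both cases are shown. What remains after adjustment is low power, noise-driven R-squared and separation, none of which an adjusted p-value cures.
- A reader might take six or seven predictors as the plan's own number. It is not; the list describes data extraction. At k=2 the problem is modest.
- A reader might infer that usability exists only in the SMS arm. The plan does not restrict the usability scale by arm, although control participants have no SMS tool to rate. It is also a 0–100 score that need not be dichotomised.
- Finding predictors is not among the Specific Aims, and nowhere is it said that regression results will set targeting or eligibility later. The risk to the next trial is therefore a possibility, not a planned use.

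What does not fall is the central point: the sentence promises independent predictors without qualification, and nothing elsewhere restricts it to something 24 people could support.

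**Conclusion.** The concern holds as a matter of reliability, not of certain failure. With 24 participants, or at most 12 for engagement, the plan must accept either a false-predictor risk of about 9% (k=2) to 24% (k=6–7) without adjustment, or power of about 18% for a moderate predictor with it (k=6). For binary outcomes in 12 people, the model becomes progressively inestimable as k passes four.

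These figures rest on an assumed k, independent predictors and f²=0.15. They are optimistic about n if the responder-only analysis sets apply. Because the pilot's aims are feasibility and acceptability, this is a change that should be made; it does not threaten the study's main purpose.

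**What to change.** Replace the sentence in the Analytical Plan with:

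> Regression is limited to the arm effect on BP and MAQ, adjusted for the baseline value of that outcome, in all randomised participants with follow-up data. Associations of participant characteristics with engagement, usability and no-show are exploratory, described one at a time with estimates and 95% CIs, without significance tests and with no claim of independent prediction.

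Two parts of this wording matter. The analysis set has to be named, because a set made up of SMS responders contains no controls if only the SMS arm is texted, and the arm effect could not then be estimated. The exploratory label and the absence of tests are needed because six or seven characteristics against three outcomes give 18–21 intervals. If these were independent, the chance that at least one excludes the null would be 1 − 0.95^18 = 60% to 1 − 0.95^21 = 66%.

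The change is to wording only and affects no data collection or participant procedure. What is lost is a list of predictors that this sample size cannot support.

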Participants will be interviewed by the study team and those with a MAQ score of 1 to 4 will be classified as non-adherent will be invited to participate. The study team member will assess the potential participant's phone ownership, text messaging ability, text messaging willingness, and receptivity to the intervention (and record all this information). The MAQ cut-off was chosen for the study because it has been used in the literature in previous studies,²⁰⁻²² and the cut-off at this value provides a highly sensitive tool for identifying medication non-adherence.^{22,23}

Participants will be randomized into one of two groups: intervention SMS arm or the control arm. If enrolled in the intervention arm, the subjects will be contacted by phone via SMS and phone call. To ensure equal access to participation among women and minorities we will translate all materials and questions to Spanish. The privacy of potential subjects during recruitment will be protected by collecting only necessary identifiers and using a private room during the interview process.

As part of routine care, patients who present to the office with uncontrolled HTN receive instructions from their clinician on medication changes and are advised to return for a nurse visit in 2 weeks and a clinician visit in 3 months. During follow-up, the nurse checks the patient's blood pressure and contacts the clinician for further management if the BP is not controlled. Participants in the SMS arm will receive SMS messages to monitor their blood pressure in addition to this routine care whereas the control arm will only receive the standard provider education and monitoring for controlling blood pressure.

Baseline demographic characteristics of the participants will be collected. Participants will be followed with office (or phone if they no show for their visit) interviews at 2 weeks or 3 months to complete 2 validated scales: the MAQ, and SUS+ free comments

Study intervention participants will be provided with a blood pressure monitor to be used for measurement and extraction of HBPM information. Clinicians will be alerted through an in-basket message in the electronic medical record (Wake One) if the participants report BP outside the threshold range, and the patient will be sent an SMS and prompted to contact their clinic. The threshold range set for SBP is between 90 and 180 mm Hg and between 60 and 110 mm Hg for DBP for one-time measurements. These thresholds are made based on the

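### The full analysis set requires an SMS reply that only the SMS arm can give, so as written it contains no controls and cannot support the between-group analyses

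*Combined protocol and SAP*

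**What the plan says.** The Analytical Plan defines one full analysis set: "The full analysis set will include participants who have responded to at least one SMS message post-randomization". It gives no separate rule for controls. The same paragraph plans summaries for each treatment group, says "95% confidence intervals will be used to summarize the differences between groups", plans a mixed linear model for BP, and adds "The Wilcoxon rank sum test will be used to compare MA between groups". An earlier sentence in that section, which names no analysis set, says "Comparison between groups will be done using chi square tests for proportions, and t-tests for continuous variables".

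The section ends with a second rule: "The primary analysis will consist of all subjects who responded with at least one BP measurement". It does not say by what route the measurement must arrive, or how this population relates to the full analysis set. No set of all randomised participants is defined.

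On who is texted, the Design section says "If enrolled in the intervention arm, the subjects will be contacted by phone via SMS and phone call", and that "the control arm will only receive the standard provider education and monitoring for controlling blood pressure". Interventions and Interactions agrees: "Participants in the SMS intervention arm will receive usual care and SMS texting and phone calls". Informed Consent describes a pamphlet and SMS as alternatives. The sample size is 24 in two groups, read here as 12 per arm.

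**The concern.** Membership of the set depends on answering a message that controls are never sent. Two readings follow, and neither supports a valid comparison.

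- **As written:** the set has no controls, so no between-group quantity can be calculated in it.
- **Controls exempted without saying so:** SMS participants must earn entry by replying, while controls enter automatically. The arms are then no longer comparable by randomisation. If people who answer texts also take their tablets and attend more reliably, the result favours SMS.

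The outcomes at stake are BP change, MAQ adherence and no-show. They are secondary, but the Specific Aims present the pilot's results as preliminary data for a later efficacy trial. Leaving the set unresolved would also let the analyst decide who counts after seeing who replied.

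**Working it through.** **1. Size of the set.** Inputs: 12 per arm (Sample Size); SMS to one arm only (Design; Interventions and Interactions). The documents give no SD, effect size or power for 24, so the only check available on that figure is 2 × 12 = 24, which agrees. With any-reply rate r, expected membership is 12 × r from the SMS arm and 12 × 0 = 0 from control.

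| r | SMS arm in set | Controls in set | Excluded of 24 |
|---|---|---|---|
| 0.50 | 6 | 0 | 18 |
| 0.75 | 9 | 0 | 15 |
| 1.00 | 12 | 0 | 12 |

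The standard error of a difference contains 1/n for each arm, so it is undefined when n = 0 for control. The t-test, chi-square and rank-sum test fail in this set for the same reason.

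**2. Controls exempted.** Assumptions, none from the documents: SD of BP change 16 mmHg; correlation ρ between a latent tendency to reply and BP improvement; the fraction r with the highest tendency reply; no true effect. The expected spurious difference (SMS responders minus all controls) is

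bias = -ρ × φ(c)/r × SD, with c = z(1 - r).

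Example: r = 0.50 gives c = 0 and φ(c) = 0.399, so the bias is -0.3 × 0.399/0.50 × 16 = -3.8 mmHg.

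| r | ρ = 0 | ρ = 0.2 | ρ = 0.3 | ρ = 0.5 |
|---|---|---|---|---|
| 0.50 | 0 | -2.6 | -3.8 | -6.4 |
| 0.75 | 0 | -1.4 | -2.0 | -3.4 |
| 0.90 | 0 | -0.6 | -0.9 | -1.6 |
| 1.00 | 0 | 0 | 0 | 0 |

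At ρ = 0.3, SD 12 to 20 gives -2.9 to -4.8 at r = 0.50 and -0.7 to -1.2 at r = 0.90. With two complete time points, the mixed model's arm-by-time contrast equals the difference in mean change, so it carries the same bias.

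The 44% cut-off under Feasibility is a home-BP response rate. It bears only on the primary-analysis sentence, and only if that means measurements sent by text. The bias is then -4.3 at ρ = 0.3 and -7.2 at ρ = 0.5.

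**3. Effect on testing.** Pooled t-test on change, 200,000 simulated trials with no true effect, SMS responders against 12 controls. The 0.0125 level is Bonferroni for an assumed four tests (0.05/4).

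| r | ρ | Rejects at 0.05 | Rejects at 0.0125 |
|---|---|---|---|
| 1.00 | any | 5.0% | 1.2% |
| 0.90 | 0.3 | 5.2% | 1.4% |
| 0.75 | 0.3 | 5.7% | 1.5% |
| 0.50 | 0.3 | 7.1% | 2.0% |
| 0.50 | 0.5 | 11.2% | 3.5% |
| 0.44 | 0.5 | 12.1% | 4.0% |

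Bonferroni lowers the rejection rate but leaves the bias in the estimate.

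**4. Imprecision for comparison.** Half-width of the 95% CI = t(0.975, n1 + n2 - 2) × 16 × √(1/n1 + 1/n2): 13.5 mmHg for 12 v 12, 14.8 for 9 v 12, 17.0 for 6 v 12. These assume every included participant has a 3-month BP. If 30% are missing (the clinic no-show rate quoted under Secondary measures of interest), about 12 × 0.7 = 8.4, say 8, per arm remain, and 8 v 8 gives 2.145 × 16 × √(2/8) = 17.2.

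**5. Is a text reply needed for the outcomes?** No. Under Secondary measures of interest, office BP comes from the medical record, the coordinator administers the MAQ, and no-show is observed.

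**The case against.** **Not every passage limits SMS by arm.** Aim 2 speaks of a single cohort of 24 for the SMS intervention, and Subject Recruitment Methods and Informed Consent describe texting enrolled participants in general. This does not rescue the definition. The Design section repeats the recruitment sentence with the intervention-arm limit added, no control-arm message is described anywhere, and the set itself refers to randomisation. It looks like text left from a single-arm design. If controls were texted, the contrast between arms would largely disappear.

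**The tests are not expressly tied to this set.** True: the chi-square and t-test sentence names no population, and a separate sentence governs the primary analysis. The harm is therefore conditional on the set being used. But the intervals, mixed model and Wilcoxon test share its paragraph, and no all-randomised set exists as an alternative. The primary-analysis sentence helps only if readings by any route count. The protocol does not say so, and the Design section is inconsistent on whether controls receive a home BP device.

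**The bias is small and assumed.** This stands in part. With zero correlation there is none, with a negative one its sign reverses, and in every scenario shown it is below the CI half-width. The main defect, however, is the empty control arm, which needs no assumption.

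**It is a feasibility pilot.** The feasibility and acceptability criteria do not fail for want of controls. They are not wholly untouched, though: an SMS response rate calculated inside this set is 100% by construction, and the no-show rate, judged against the 30% clinic figure, would be calculated in responders only.

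**Conclusion.** The concern holds, with high confidence, and must be fixed. As written, the only defined full analysis set contains 0 of 12 controls and cannot yield the between-group results planned beside it. That conclusion rests on the text alone.

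If controls are exempted, the comparison is open to selection bias: 0 to -6.4 mmHg for reply rates of 50% to 100% and correlations of 0 to 0.5, with an assumed SD of 16 mmHg. The size and direction are illustrative. The bias is smaller than the trial's imprecision, but it is systematic and can be avoided. The damage falls on the between-arm BP, MAQ and no-show results, not on the feasibility and acceptability aims as such.

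**What to change.** Replace both analysis-set sentences in the Analytical Plan.

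1. Analyse SBP, DBP, MAQ and no-show in all randomised participants as assigned, whether or not they replied to any SMS. Use all available follow-up data (for BP, in the planned mixed model), and report missing 3-month values with reasons by arm.
2. Keep responders only as a labelled descriptive subset of the SMS arm.
3. State that SMS response, engagement and retention use everyone assigned to SMS as denominator, with non-responders counted as not engaged. State that the usability criterion is assessed in the SMS arm, and report the number who did not complete it.
4. Reconcile with the two-arm design the wording not limited by arm in Aim 2, Subject Recruitment Methods and Informed Consent, and the two statements in the Design section on who receives a BP device.

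The cost is wording only, with no new data. The engagement figure may look less favourable, and missing 3-month BP and MAQ values will have to be shown by arm. Because a missed visit is followed up by telephone, office BP will still be incomplete for some participants. The change removes selection on SMS reply; it does not remove missing data.

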1. Screening: we will track the number of patients screened per month, the number enrolled per month, the proportion that are eligible who enroll.
2. Recruitment: number of participants who refuse to participate in the pilot at the time of recruitment and the reason why. Proportion of vulnerable patients screened but excluded because they did not own a phone with SMS capability.
3. Retention: the proportion of participants who continue to use the myHealth tool per month through three months will be tracked for the intervention.
4. Engagement: 12- SMS rate response of at least one home BP measurement. We will use 44% as our cut off based on an SMS study by Peters and colleagues²⁵.

Finally, we will monitor time needed for assessments and gather feedback on the participant burden.

B-Acceptability

Participants will complete the SUS in person on an I-Pad or over the phone. They will also be offered the opportunity to comment in their questionnaires about their experiences of taking part in the pilot. The SUS yields a single score on a scale of 0–100. A SUS score above a 68 would be considered above average. We will consider acceptable when >70 % of participants score the SUS above 68.²⁶

Secondary measures of interest

Medication adherence (MA) will be measured by administrating the four-item MAQ by the study coordinator during enrollment and at 3 months follow up visit. The MAQ was selected because it has been well-validated to identify adherence in HTN and scores have been shown to correlate well with a range of objective adherence measures.^{11,12}

SBP and DBP change at 3 months. BP will be measured during initial and follow up office visits by nurses or clinicians while patient is seated with automated arm devices according to standard office procedures. We will extract from the electronic medical record, SBP and DBP at enrollment and at 12 weeks follow up. The average change will be calculated and reported in mmHg.

No-show rate at 3 months' follow-up (f/u) clinic visits. If participants fail to come to their f/u visits within 7 days of their scheduled follow-up appointment, they will be considered as "no-shows". Our current clinic no-show rate is 30%, therefore if the study participants no-show rate is less than 30% we will consider our tool a feasible intervention.

Analytical Plan

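### Confidence intervals are planned only for between-group differences, so the SMS-arm proportions that decide feasibility and acceptability have no interval and no defined denominator

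*Combined protocol and SAP*

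**What the plan says.** **Analysis.** The Analytical Plan has one sentence on intervals: "For primary and secondary outcomes, descriptive statistics and 95% confidence intervals will be used to summarize the differences between groups". Proportions are to be compared between groups by chi-square. For each arm separately it promises: "Descriptive statistics will be computed for each treatment group; medians and percentiles will be reported for skewed continuous variables". It names no one-sample interval and no one-sample test. Testing follows the rule "Hypothesis tests will be 2-sided using the 0.05 significance level", with a Bonferroni-type adjustment over a number of tests that is not given.

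**Outcomes.** No outcome is explicitly labelled primary. Feasibility and acceptability are listed before the secondary measures, so they are primary by implication.
- Engagement (Outcome Measures, A) is an SMS reply giving a home BP reading, with a 44% cut-off.
- Retention (Outcome Measures, A): "the proportion of participants who continue to use the myHealth tool per month through three months will be tracked for the intervention". No cut-off is given.
- Acceptability (Outcome Measures, B): "We will consider acceptable when >70 % of participants score the SUS above 68".
- The first hypothesis (Specific Aims) "is that over 50% of contacted patients will respond to SMS messages and over 50% will check HBPM". The second is that more than 75% rate the service OK or better.
- No-show, a secondary measure, has a feasibility rule of below 30%.

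**Arms.** Under Design, the SMS arm gets texts on top of routine care, "whereas the control arm will only receive the standard provider education and monitoring for controlling blood pressure".

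**Analysis sets.** The full analysis set is limited to people who replied to a text after randomisation. The primary analysis is limited to those who responded with a BP measurement.

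**The concern.** The decision rules and the planned inference do not match. The pilot is judged by single-group proportions set against fixed cut-offs, while every stated interval and test compares two groups. A control participant cannot reply to a text, go on using the tool, or rate a service never received. For these outcomes the planned difference has no useful meaning, and the quantity that drives the decision has no stated uncertainty.

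The Specific Aims present the pilot as the source of preliminary data for a later efficacy trial. A bare pass or fail from about 12 people could be carried into that application as if it were well established.

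**Working it through.** **Inputs.** The Sample Size section gives 24 patients and "We will randomize 12 patients into 2 groups", read here as 12 per arm (2 × 12 = 24). No power, precision or effect size is given, so no calculation behind 24 can be reproduced. The cut-offs are those listed above.

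**Step 1: smallest passing count, n = 12.**
- 44%: 0.44 × 12 = 5.28, so 6.
- Over 50%: 0.50 × 12 = 6, so 7.
- Over 70%: 0.70 × 12 = 8.4, so 9.
- Over 75%: 0.75 × 12 = 9, so 10.
- No-show below 30%: 0.30 × 12 = 3.6, so at most 3.

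**Step 2: exact interval.** The Clopper-Pearson lower limit L solves P(X ≥ x | n, L) = 0.025. The upper limit U solves P(X ≤ x | n, U) = 0.025.

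**Step 3: chance of passing when the true rate equals the cut-off c.** This is the sum over k ≥ x of C(12,k) c^k (1 − c)^(12 − k). For no-show the sum runs over k ≤ 3.

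| Outcome (SMS arm) | Cut-off | Just passes | Exact 95% CI | P(pass) at cut-off |
|---|---|---|---|---|
| Engagement | 44% | 6/12 = 50% | 21.1–78.9% | 0.445 |
| SMS response | >50% | 7/12 = 58.3% | 27.7–84.8% | 0.387 |
| SUS above 68 | >70% | 9/12 = 75% | 42.8–94.5% | 0.493 |
| Satisfied (OK or better) | >75% | 10/12 = 83.3% | 51.6–97.9% | 0.391 |
| No-show | <30% | 3/12 = 25% | 5.5–57.2% | 0.493 |

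Every interval contains its own cut-off. The four engagement and usability intervals are between 46.3 points (97.9 − 51.6) and 57.8 points (78.9 − 21.1) wide. For the exact lower limit to clear the cut-off would take 10/12 for 44%, 10/12 for 50% and 12/12 for 70%. No count out of 12 achieves it for 75%.

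**Step 4: sensitivity to n.** Aim 2 speaks of 24 people in the SMS cohort, which conflicts with 12 per arm. At n = 24 the smallest passing results are 11/24 = 45.8% (CI 25.6–67.2%) for engagement and 17/24 = 70.8% (CI 48.9–87.4%) for SUS. Both intervals still contain their cut-offs.

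**Step 5: effect of the analysis sets.** Suppose 5 of the 12 people randomised to SMS text a reading. Over everyone randomised, engagement is 5/12 = 41.7%, which fails 44%. In a set restricted to people who sent a reading it is 5/5 = 100%. The exact lower limit is then 0.025^(1/5) = 0.478, above 44%. An interval added without defining n would therefore make a failed criterion look secure.

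**The case against.** **The estimates are already planned.** This stands. Per-arm descriptive statistics and the stated cut-off rules imply the SMS-arm proportion and its comparison with the cut-off. Retention is already described as an intervention-arm quantity. What is missing is the interval, and a reader given x and n could compute it. The interval alone would change no pass or fail, because the rules use point estimates.

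**A stronger reading is tempting:** that the primary result would be a significant test against controls who are zero by construction. For 5/12 against 0/12, chi-square = 24 × (5 × 12)² / (12 × 12 × 5 × 19) = 6.32, p = 0.012 (Fisher p = 0.037), although 5/12 misses the 44% cut-off. The documents do not support this as what the plan would do.
- Controls who are not texted do not enter analysis sets defined by replying, so the 5/12 against 0/12 table would not literally be formed.
- The Bonferroni-type adjustment covers an unstated number of tests. With two tests (0.05/2 = 0.025) the Fisher p-value already fails. With five (0.05/5 = 0.01) the chi-square p-value fails too.

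**The SUS may be meant for the SMS arm only.** Probably so: Aim 2 ties it to the SMS intervention. Design and the acceptability section say only that participants complete it. This is an ambiguity, not a stated plan to survey controls.

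**Some outcomes exist in both arms.** Agreed for no-show, MAQ and BP. Checking BP at home may also exist in both arms, since Design gives a device to all participants in one place and to intervention participants in another. Engagement is nevertheless defined as an SMS reply.

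**Conclusion.** The concern holds as a mismatch between the decision rules and the planned inference. For engagement, SMS response, tool retention and SUS acceptability, the only planned interval belongs to a contrast that cannot be interpreted, and the SMS-arm proportion has none. At 12 per arm, just-passing results carry exact intervals of 21–79% (engagement) and 43–95% (SUS). A point-estimate rule passes with probability 0.445 and 0.493 respectively when the true rate only equals the cut-off.

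The analysis sets add a second problem: they remove controls who are not texted and lift engagement towards 100% by construction.

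This rests on three readings: 12 per arm; feasibility and acceptability as the primary outcomes; and the primary analysis set meaning a reading sent in reply to a text. If an office reading qualified, controls could enter that set, but the full analysis set would still require an SMS reply.

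This should be fixed before analysis. It does not affect randomisation or data collection, and it does not show that the plan would declare a false positive.

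**What to change.** Replace the interval sentence in the Analytical Plan with wording such as:

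> Engagement, SMS response, tool retention and SUS acceptability are estimated in the SMS arm only, as x/n with an exact (Clopper-Pearson) 95% CI shown beside each stated cut-off. Here n is all participants randomised to SMS, and non-responders count as not engaged. For SUS, the number completing it is also shown. No between-group test is made for these outcomes. Between-group differences with 95% CIs, in all randomised participants, are reported for no-show, MAQ, SBP and DBP. The SMS-arm no-show rate is also given with an exact 95% CI beside the 30% rule.

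State in the acceptability section that the SUS is given to the SMS arm only. Bring the full and primary analysis sets into line with these denominators, and settle whether the SMS arm has 12 or 24 people.

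The cost is plan wording and a line of code, with no extra participants, visits or data. The downside is that the report will show wide intervals around every success proportion.
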